- If  $\leq 1$  of the initial 6 subjects experience a DLT, then dose expansion will commence.
- If  $\geq 2$  of the initial 3 subjects or  $\geq 2$  of the 6 total subjects experience a DLT, enrollment at DL -1 will commence.

[figure not shown]
Dose de-escalation DL -1 (1 x  $10^{11}$  VP):

- If  $\leq 1$  of the initial 6 subjects experience a DLT, this dose level will be defined as the MTD and dose expansion will commence.
- If  $\geq 2$  of the initial 3 subjects or  $\geq 2$  of the 6 total subjects experience a DLT, enrollment at DL -2 will commence.

Dose de-escalation DL-2 (5 x  $10^{10}$  VP):

- If  $\leq 1$  of 6 subjects experience a DLT, this dose level will be defined as the MTD and dose expansion will commence.
- If  $\geq 2$  of the initial 3 subjects, or if  $\geq 2$  of a total 6 subjects at DL -2 experience a DLT, dosing will be suspended, and the study will be re-evaluated.

# 3.2 ETBX VACCINE DOSE PREPARATION

The dose of each ETBX vaccine to be injected is  $5 \ge 10^{11}$  VP per 1 mL. Dose levels of  $1 \ge 10^{11}$  VP per mL (dose level -1), or  $5 \ge 10^{10}$  VP per mL (dose level -2) are available for de-escalation. Prior to injection, the appropriate vial should be removed from the freezer and allowed to thaw at controlled room temperature (20–25°C, 68-77°F) for at least 20 minutes and not more than 30 minutes, after which it should be kept at 2-8°C (35–46°F).

Each vial is sealed with a rubber stopper and has a white flip-off seal. The end user of the product will need to flip the white plastic portion of the cap up/off with their thumb to expose the rubber stopper and then puncture the stopper with an injection needle to withdraw the liquid. The rubber stopper is secured to the vial with an aluminum-crimped seal.

The thawed vial should be swirled and then, using aseptic technique, the pharmacist or pharmacist designee should withdraw the appropriate volume from the appropriate vial using an appropriately sized syringe.

The vaccine dose should be injected as soon as possible using a 1 to 1/2 inch, 20 to 25-gauge needle. If the vaccine cannot be injected within 1 hour, the syringe should be returned to the pharmacy and properly disposed in accordance with institutional policy and procedure, and disposition must be recorded on the investigational product accountability record.

Note that storage of the vaccine in the vial at  $2-8^{\circ}C$  (35–46°F) must not exceed 8 hours. Also, once the vaccine has been thawed, it must not be refrozen, and, if not used, it should be disposed of as described above.

# **3.2.1** Instructions for Dose Preparation – 5 x 10^11 Virus Particles

Withdraw 1 mL of contents from the vial, prepare the injection site with alcohol, and administer to the subject by SC injection in the thigh without any further manipulation (refer to the vial label for a description of the vialed ETBX vaccine concentration).

# **3.2.2** Instructions for Dose Preparation – 1 x 10^11 Virus Particles

Withdraw 0.2 mL of contents from the vial, prepare the injection site with alcohol, and administer to the subject by SC injection in the thigh without any further manipulation (refer to the vial label for a description of the vialed ETBX vaccine concentration).

# 3.2.3 Instructions for Dose Preparation – 5 x 10^10 Virus Particles (For Dose De-escalation)

From a 5.0-mL vial of 0.9% sodium chloride for injection, remove 0.5 mL of fluid using a 1.0 mL tuberculin syringe, leaving 4.50 mL. Then, using another 1.0 mL tuberculin syringe, remove 0.5 mL from the vial labeled ETBX-071, ETBX-061, or ETBX-051, respectively, and deliver this volume into the 4.50 mL of sterile saline remaining in the 5-mL sterile saline vial. Mix the contents by inverting the 5 mL of diluted ETBX vaccine. Then withdraw 1 mL of the diluted ETBX vaccine, prepare the injection site with alcohol, and administer to the subject by SC injection in the thigh (refer to the vial label for a description of the vialed ETBX vaccine concentration). Alternatively, 4.5 mL of 0.9% sodium chloride for injection may be added to an appropriately sized sterile empty vial (e.g. 10 mL) using an appropriately sized syringe. Then, using a new syringe, remove 0.5 mL from the vial labeled ETBX-071, ETBX-061, or ETBX-051, respectively and deliver this volume into the sterile vial containing the 4.5 mL 0.9% sodium chloride for injection. Mix the contents by

inverting the 5 mL of diluted ETBX vaccine. Then withdraw 1 mL of the diluted ETBX vaccine, prepare the injection site with alcohol, and administer to the subject by subcutaneous injection in the thigh (refer to the vial label for a description of the vialed ETBX vaccine concentration).

# 3.2.4 Administration

ETBX-051, ETBX-61 and ETBX-71 vaccines will be administered on Weeks 0, 3, and 6 for a total of three injections. In dose expansion, ETBX-051, ETBX-61 and ETBX-71 vaccines will be administered on Weeks 0, 3, and 6 for a total of three injections followed by booster injections at 8-week intervals for up to 1 year. All study drug administration treatments should occur within  $\pm$  7 days of the planned visit date. Treatment may be shorter for patients who experience progressive disease (unequivocal or confirmed) or unacceptable toxicity, withdraw consent, or if the Investigator feels it is no longer in their best interest to continue treatment.

The vaccines will be administered subcutaneously as 3 separate injections preferably in the anterolateral section of the same thigh separated from each other by a minimum of 5 cm. It is also preferred to administer ETBX-071 most proximal, ETBX-061 in the middle, and ETBX-051 most distal and the injected thigh should be alternated each treatment visit when possible.

# 3.2.5 Other Considerations

The Ad5 [E1-, E2b-] vector is non-replicating and its genome does not integrate into the human genome. However, since this is a non-replicating recombinant virus, we recommend that it be handled under Biosafety Level-2 conditions. Any vialed ETBX vaccine material that has been used in the study should be autoclaved or incinerated after use according to institutional policy and according to local, state, and federal regulations. Refer to the Material Safety Data Sheets for additional handling instructions.

3.3 Dose Modifications and Delays

# 3.3.1 Dosing Delay (applies to events occurring outside of the DLT evaluation period)

Patients must have recovered to  $\leq$  grade 2 for injection site reaction or grade  $\leq$  1 for any other toxicity related to the vaccines for the parameters used to assess levels of organ function required for eligibility (see Section 2) after each vaccination in order to receive a subsequent vaccination (see Sections 2.1.1.7 and 2.1.1.8).

If  $\geq$  grade 3 nonautoimmune toxicity attributable to the vaccines persists for > 42 days, the patient will not receive further vaccine inoculations and will be removed from the protocol treatment and followed for resolution of toxicity and immune/survival endpoints.

Patients who develop grade 3 injection site reactions will have their vaccines held until injection site reaction resolves to grade 2 or less. Patients will receive a diary card to record injections site reactions (see **Appendix B**).

Patients who develop  $\geq$  a grade 2 allergic or autoimmune disease that threatens vital organ function or any  $\geq$  grade 3 autoimmunity, not related to a therapeutic response, will be removed from the protocol treatment and followed for resolution of toxicity and immune/survival endpoints.

Patients who develop any grade 4 toxicity attributable to the vaccines will be removed from the protocol treatment and followed for resolution of toxicity and immune/survival endpoints.

For unrelated acute illnesses present at the time of a scheduled vaccination, dosing can be delayed until symptoms subside, or the subject may be withdrawn at the discretion of the Investigator; delays up to 4 weeks are considered acceptable in this setting.

If a scheduled vaccine dose is missed due to scheduling or logistical issues, the vaccine may be given within 7 days of the appointed time.

# **3.3.2 Dose Modifications**

No dose modifications are allowed with these vaccines except for dose cohort de-escalation as described in section **3.1**.

Title: Ad5-based vaccines in mCRPC	: 09.20.2018
Ad5-l	09.2
Title:	ate
Abbreviated	NCI Version D

# 3.4 STUDY CALENDAR

Assessment	Screening 	Treatment (Every 3-W	Treatment (Every 3-Week Dosing)	g)	Bi-monthly Boosters (every 8 weeks – only expansion cohort) p	End of Treatment (within 90 days after the last vaccine) k	Post Study Therapy Follow Up
Study Week	Day -28 to -1	Baseline/ Wk-0	Wk-3	Wk-6	Week 14, 22, 30, 38, 46, 54		
Clinic Visit	X	Х	X	Х	X	X	
Informed Consent 	Х						
Inclusion/Exclusion	Х						
Demographics	Х						
Physical Examination, Height a , Weight, ECOG	Х	$X^{ ho}$	X	Х	Х	Х	
Medical History c	Х	Х					
Concomitant Medications	Х	Х	Х	Х	Х	Х	
Vital Signs d	Х	Х	Х	Х	Х	Х	
12-Lead ECG	Х				Х	X	
Confirm Contraceptive Measures c	Х						
Study Drug Injection/ Injection Site Reaction Monitoring f		Х	X	Х	Х		

41

tle: Ad5-based vaccines in mCRPC	:: 09.20.2018
Abbreviated Title:	NCI Version Date: 6

Assessment	Screening 	Treatment (Every 3-W	Treatment (Every 3-Week Dosing)	g)	Bi-monthly Boosters (every 8 weeks – only expansion cohort) p	End of Treatment (within 90 days after the last vaccine) k	Post Study Therapy Follow Up
Study Week	Day -28 to -1	Baseline/ Wk-0	Wk-3	Wk-6	Week 14, 22, 30, 38, 46, 54		
Dispensation of Subject Diary Card g		X					
Review of Subject Diary Card g			Х				
Tumor Imaging/CT scan and bone scan h	Х				Х		
Urinalysis	$X^{l}$					Х	
Chemistry Panel m	$\mathbf{X}^{\mathrm{l}}$	$\mathbf{X}^{\mathrm{b}}$	Х	Х	Х	X	
CBC, Differential, Platelets	X 	$X^{ ho}$	Х	Х	Х	Х	
Serum PSA and testosterone level	X	Х	X	X	Х	Х	
PT/INR, PTTT	$X^{l}$					Х	
Serum Virology (HIV, HBV, HCV) i	Х						
Adverse Events		Х	Х	Х	Х	Х	
Exploratory Immune Analysis		Х		X	X (only week 14 and 30)	Х	
Telephone Follow Up j							X

itle: Ad5-based vaccines in mCRPC	· 09.20.2018
Title:	Date:
Abbreviated	NCI Version

Assessment	Screening 	Treatment (Every 3-W	Freatment (Every 3-Week Dosing)	d (S	Bi-monthly Boosters (every 8 weeks – only expansion cohort) p	End of Treatment (within 90 days after the last vaccine) k	End of Treatment Post Study (within 90 Therapy Follow days after the Up last vaccine) k
Study Week	Day -28 to -1	Baseline/ Wk-0	Wk-3	Wk-6	Week 14, 22, 30, 38, 46, 54		
Confirmation of diagnosis (path report) n	Х						

Informed consent may be obtained on D0 after eligibility is confirmed and other screening protocols may be used to obtain screening labs and procedures as per NCI's internal SOP

a Height will only be assessed at screening.

b If the assessment was performed within 24 hours prior to the first dosing, a second assessment at baseline/week 0 can be omitted.

c Complete medical history will be evaluated at screening and includes current and past cardiac and pulmonary history, documentation of diagnosis including history of current and prior cancers, prior treatment(s), and prior radiologic studies. Any new events in the medical history will be evaluated at baseline.

d Vital signs include temperature, heart rate, blood pressure, and respiratory rate. Vital sign assessments are to be obtained after the subject has been in a seated resting position for at least 5 minutes. For the first injection, vital signs must be assessed 30 and 60 minutes after the injection. Vital signs must be assessed 30 minutes after the subsequent injections.

e Contraceptive measures are described in **2.1.1.9**.

f Injection site reactions will be monitored.

g Subjects will be given a diary card for the self-evaluation and reporting of injection site reactions, see Section Appendix B. Local injection site reactions are expected to occur over several days after vaccination. Erythema and some soreness are possible. Injection site reactions will be monitored by clinic staff after each dose prior to discharge and by subject self-evaluation and reporting. Subjects will be given a diary card with reporting fields for diameter of erythema and duration (see Appendix B). In addition, pain at the injection site, fever, and chills will be collected as Yes/No and medications (over-the-counter ibuprofen, acetaminophen, aspirin, etc.) taken for injection site pain or discomfort as Yes/No. The site h All baseline tumor measurements should be performed based on the subject's qualifying scan obtained within 28 days prior to the start of treatment. staff will review the diary cards with the subject during the next clinic visit and record responses in the case report form.

Tumor imaging and assessments will be performed as described in Section 6.3. Tumor imaging may be performed +/-5 days from the next treatment for logistical and scheduling purposes.

Serum virology test for HIV (as determined by ELISA and confirmed by western blot), and HBV and HCV (as determined by HBsAg and hepatitis C serology) can be performed up to 12 weeks prior to enrollment.  After the subject completes or withdraws from study therapy, the study team will contact the subject approximately every 3 months for 12 months and then approximately every 6 months every 6 months for 24 months and then every 12 months thereafter for another 24 months to collect followup information, including survival status and any current cancer treatment regimen.

k If the patient cannot return to the Clinical Center within 90 days after the last vaccine, the patient will be contacted by phone to AEs and laboratory assessments will be deferred until a later point if at feasible.

Should be performed within 16 days prior to enrollment.

m Chemistry include acute care panel (sodium, potassium, chloride, bicarbonate, creatinine, glucose, BUN, eGFR) and hepatic panel (alkaline phosphatase, ALT, AST, Total Bilirubin, Direct Bilirubin. Blood work may be obtained +/-5 days from the next treatment day for logistical and scheduling purposes

"Confirmation of diagnosis by NCI Laboratory of Pathology or Walter Reed National Military Medical Center can be done at any time prior to enrollment.

days: -3 days up to +3 days) intervals for 3 doses then every 8 weeks (56 days: -3 days up to +8 days) intervals thereafter (treatment may be p Initial cohort: Treatment every 3 weeks (21 days: -3 days up to +3 days) intervals for 3 doses. Expansion cohort: Treatment every 3 weeks (21 delayed up to 8 days for special circumstances like severe weather, travel delays or patient event/vacation).

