# 6.3 RESPONSE CRITERIA

For the purposes of this study, patients should be re-evaluated for response at week 14 and every 8 weeks thereafter and at the of study treatment. In addition to a baseline CT and bone scan, confirmatory scans should also be obtained up to 6 (not less than 4) weeks following initial documentation of objective response.

Response and progression will be evaluated in this study using the new international criteria proposed by the revised Response Evaluation Criteria in Solid Tumors (RECIST) guideline (version 1.1; Eisenhauer 2009). Changes in the largest diameter (unidimensional measurement) of the tumor lesions and the shortest diameter in the case of malignant lymph nodes are used in the RECIST criteria.

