# 8.4.3.2 Progression-Free Survival (PFS)

PFS will be evaluated by dose cohort and overall using Kaplan-Meier methods. PFS will be defined as the time from the date of first treatment to the date of disease progression or death (any cause) whichever occurs first. Subjects who do not have disease progression or have not died at the end of follow up will be censored at the last known date the subject was progression free.

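### The imaging window in calendar footnote h is counted from the next treatment, while Section 6.3 fixes the weeks; in the expansion cohort scan dates may therefore follow held doses, with a modest average effect on PFS

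*Combined protocol and SAP*

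**What the plan says.** **Imaging schedule.** Section 6.3 says "patients should be re-evaluated for response at week 14 and every 8 weeks thereafter" and gives no window. The calendar grid places imaging in the booster column, headed "Week 14, 22, 30, 38, 46, 54".

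**Imaging window.** Footnote h says "Tumor imaging and assessments will be performed as described in Section 6.3", and the next sentence adds "Tumor imaging may be performed +/-5 days from the next treatment for logistical and scheduling purposes". This is the only on-treatment imaging window in the protocol.

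**Dosing windows.** Footnote p spaces doses by interval: 21 days, -3/+3, for the first three doses, and in the expansion cohort "then every 8 weeks (56 days: -3 days up to +8 days) intervals thereafter". Sections 3.2.4 and 11.1.5 instead hold every administration to within 7 days either side of the planned visit date.

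**Holds.** For an unrelated acute illness, Section 3.3.1 states "delays up to 4 weeks are considered acceptable in this setting". Vaccination also waits for recovery from related toxicity.

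**Boosters.** Only the expansion cohort receives doses after week 6 (Section 3.1 and footnote p).

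**PFS.** Section 8.4.3.2 runs PFS from first treatment to progression or death, by Kaplan-Meier, and censors at the last date known to be progression free. It has no rule for late or off-schedule scans.

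**The concern.** Radiographic progression is dated by the scan that shows it, so the timing of scans is part of the measurement. If a scan may move with a held dose, the assessment date depends on the subject's toxicity or illness. The interval that contains the hold is stretched, and progression inside it is found later. The average error is therefore upward, in the flattering direction, and is concentrated in subjects who had trouble with treatment. Disease control, which requires stable disease for at least 6 months, is read from the same scans.

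Two sites or two coordinators could also comply in different ways: one scanning on the planned week under Section 6.3, the other waiting for the delayed booster under footnote h. In a cohort of 12 this adds avoidable irregularity.

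**Working it through.** The plan states no PFS median, event count or precision, so there is no figure of its own to reproduce. The check has three parts.

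**1. What each anchor allows for the first scan.**
- Week 14 is day 14 × 7 = 98. A window of 5 days either side of the scheduled week gives days 93 to 103.
- If the week-14 dose is held 28 days (the illness limit in 3.3.1), it falls on day 98 + 28 = 126, and the footnote h window is days 121 to 131.
- The two windows do not overlap. A scan on day 126 complies with footnote h and is 4 weeks off Section 6.3.
- In the initial cohort the last dose is at week 6, so there is no next treatment from which to count.

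**2. One 28-day hold before the week-14 dose.** Planned scans fall on days 98, 154, 210 and so on. Because footnote p is interval-based, the moved scans fall on days 126, 182, 238 and so on.
- True progression by day 98: dated 126 instead of 98, 28 days later.
- Progression on days 99 to 126: dated 126 instead of 154, 28 days *earlier*.
- Progression on days 127 to 154: dated 182 instead of 154, 28 days later. The pattern then alternates.

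Assume exponential progression with rate λ = ln 2 / median and S(t) = exp(-λt), with 30.4375 days per month. Then

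P(earlier) = S(98) / (1 + S(28)), and mean shift = 28 × (1 - 2 × P(earlier)).

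| True median (assumed) | S(98) | S(28) | P(earlier) | Mean shift |
|---|---|---|---|---|
| 3 months | 0.475 | 0.809 | 0.475/1.809 = 0.263 | 28 × (1 - 0.526) = +13.3 days |
| 6 months | 0.689 | 0.899 | 0.689/1.899 = 0.363 | 28 × (1 - 0.726) = +7.7 days |

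A held subject thus gains on average, but by less than half the hold, and about 26% to 36% of held subjects are dated earlier.

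**3. Whole-cohort effect.** Simulation with these assumptions, none of them from the documents except the windows: exponential progression; dose intervals uniform within the footnote p windows; a stated chance of a 28-day delay at each dose after the first; the scan on the day of the booster; progression dated at the first scan on or after it. The comparator is scans on the fixed weeks. The outcome is restricted mean PFS to week 54.

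| True median | Fixed weeks | Dose-linked, 10% to 20% delayed | Rise |
|---|---|---|---|
| 3 months | 23.7 | 24.6 to 25.3 | 0.9 to 1.6 weeks |
| 4 months | 27.3 | 28.1 to 28.7 | 0.8 to 1.4 weeks |
| 6 months | 32.8 | 33.4 to 33.9 | 0.6 to 1.1 weeks |

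With a delay chance of 0 to 2% per dose, the rise over the same three medians is about 0.1 to 0.4 weeks.

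**The case against.** **The footnote is permissive.** It says imaging *may* be done in that window, for logistical reasons, straight after deferring to Section 6.3. 'Next treatment' could even mean the next scheduled one. A reader might infer that a held dose must carry the scan with it. The text does not say so, and a site can still scan on the planned week. What stands is that both practices comply and nothing separates the scan from a held dose.

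**Drift from the dosing windows is not settled.** A reader might add up the footnote p tolerances dose by dose and conclude that late scans drift by many weeks. Sections 3.2.4 and 11.1.5 tie each dose to its planned date, which caps ordinary drift. The passages conflict, so the accumulated reading cannot be taken as the rule. Part 3 above uses footnote p and is on the generous side for that reason.

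**Six weeks is not a permitted dose delay.** A reader might take it from the removal rule, "nonautoimmune toxicity attributable to the vaccines persists for > 42 days, the patient will not receive further vaccine inoculations". That limit is the duration of a toxicity, not lateness past a due date. With boosters 56 days apart, much or all of such an episode can pass before the next dose is due.

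**The median need not rise.** With fixed scans the estimated median can only fall on a scan date. Under the same model it rises for an assumed true median of 3 months and falls for one of 3.25 months. No claim about the median is supported.

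**Reach and use are limited.** Only the 12 expansion subjects have boosters, not all 18 planned at the MTD. PFS is a secondary, preliminary, single-arm description, and no test or decision rests on it. The documents give no delay rate either: the earlier trial of the same vector, summarised in Sections 1.2.6.1 and 11.1.2, reports mainly self-limited reactions, which favours the low end of the range. All of this stands, and it sets the severity.

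**Conclusion.** The inconsistency is real and minor. Footnote h and Section 6.3 give two unreconciled anchors for the same scans. In the expansion cohort, assessment times are allowed to depend on toxicity or illness; in the initial cohort the window has no anchor.

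The likely consequence is a small upward shift in average PFS: about 0.1 to 0.4 weeks of restricted mean if long delays are rare, and about 0.6 to 1.6 weeks if 10 to 20% of doses are delayed by 28 days. These sizes rest on the assumed exponential progression, true medians of 3 to 6 months, the footnote p windows, and scans always following the dose. The documents do not support saying that every held subject's PFS is lengthened, that the gain equals the hold, or that the median moves in a known direction.

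Separately, the dosing windows in footnote p and in Sections 3.2.4 and 11.1.5 disagree and must be reconciled.

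**What to change.** In footnote h, replace the words that count the window from the next treatment with: *of the scheduled week (14, 22, 30, 38, 46, 54) counted from the first vaccination, whether or not a dose is given on time*. This agrees with Section 6.3 and should apply to both cohorts, which also gives the initial cohort an anchor. State in Section 8.4.3.2 that progression is dated by the actual scan date. Reconcile the dosing windows in footnote p with those in Sections 3.2.4 and 11.1.5; this review takes no view on which is right.

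The cost is one footnote and one sentence, plus an occasional scan visit without an injection when a dose is late. No dose or hold rule needs to change for the imaging fix.

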# 2 ELIGIBILITY ASSESSMENT AND ENROLLMENT

2.1 ELIGIBILITY CRITERIA

# 2.1.1 Inclusion Criteria

- 2.1.1.1 Age  $\geq$  18 years (male).
- 2.1.1.2 Ability to understand and provide signed informed consent that fulfills Institutional Review Board (IRB)'s guidelines.
- 2.1.1.3 Cytologically or histologically confirmed prostate cancer for which no curative standard approved therapy is available by either the Laboratory of Pathology at the NIH Clinical Center or Walter Reed National Military Medical Center at Bethesda prior to starting this study. If no pathologic specimen is available, patients may enroll with a pathologist's report showing a histological diagnosis of prostate cancer and a clinical course consistent with the disease.
- 2.1.1.4 Eastern Cooperative Oncology Group (ECOG) performance status of 0 to 1.
- 2.1.1.5 Subjects who have received prior PSA, MUC1, and/or brachyury-targeted immunotherapy (e.g. vaccine) are eligible for this trial if this treatment was discontinued at least 3 months prior to enrollment.
- 2.1.1.6 Resolution of all toxic side effects of prior chemotherapy, radiotherapy, or surgical procedures to NCI CTCAE Grade  $\leq 1$ .
- 2.1.1.7 Adequate hematologic function at screening, as follows:
  - Absolute neutrophil count (ANC)  $\geq 1.0 \times 10^{9}/L$
  - Hemoglobin  $\ge 9 \text{ g/dL}$
  - Platelets  $\geq$  75,000/microliter.

- Prothrombin (PT)-international normalized ratio (INR) < 1.5.
- Partial thromboplastin time (PTT) < 1.5 x upper limit of normal (ULN).
- 2.1.1.8 Adequate renal and hepatic function at screening, as follows:
  - Serum creatinine ≤ 1.5 x upper limit of normal (ULN) OR creatinine clearance (CrCl) ≥ 40 mL/min (if using the Cockcroft-Gault formula below):

a) Female CrCl = [(140 - age in years) x weight in kg x 0.85] / [72 x serum creatinine in mg/dL]

b) Male CrCl = [(140 - age in years) x weight in kg x1.00] / [72 x serum creatinine in mg/dL]

- Total bilirubin  $\leq$  1.5 x ULN OR in subjects with Gilbert's syndrome, a total bilirubin  $\leq$  3.0 x ULN
- Alanine aminotransferase (ALT) and aspartate aminotransferase (AST)  $\leq 2.5 \times ULN$ , unless liver metastases are present, then values must be  $\leq 5 \times ULN$ )

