2.4 BASELINE EVALUATION

All subjects are required to complete baseline evaluations within 1 day prior to the first planned dosing of the study drug (Any screening evaluation done on D-1 of treatment can also serve for

the baseline evaluation). The following procedures and evaluations will be performed and documented in the subject's source records.

- History and physical exam, including weight, ECOG status and vital signs
- Hepatic Panel (Alkaline Phosphatase, ALT/GPT, AST/GOT, Total Bilirubin, Direct Bilirubin)
- Acute Care Panel (Sodium [NA], Potassium [K], Chloride [CL] Total CO2 [Bicarbonate], Creatinine, Glucose, Urea nitrogen, eGFR)
- CBC with differential
- PSA and testosterone

If these assessments have been previously performed within 24 hours prior to the first dosing, a second assessment at baseline/week 0 can be omitted.

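### Blood tests for a repeat dose may be drawn up to 5 days after the injection, although re-dosing depends on recovery of the same laboratory parameters

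*Combined protocol and SAP*

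**What the plan says.** **Recovery condition.** Section 3.3.1 requires vaccine-related toxicity to have returned to grade 2 or less (injection-site reactions) or grade 1 or less (other toxicity in the organ-function eligibility parameters) "after each vaccination in order to receive a subsequent vaccination". It points to 2.1.1.7 (ANC, hemoglobin, platelets, PT-INR, PTT) and 2.1.1.8 (creatinine or creatinine clearance, bilirubin, ALT, AST). Its heading limits the section: it "applies to events occurring outside of the DLT evaluation period".

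**Scheduled tests.** The calendar in 3.4 lists the chemistry panel and the row "CBC, Differential, Platelets" at weeks 3 and 6 and at each booster. It lists no other chemistry or CBC between doses.

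**Draw window.** Footnote m, marked on the chemistry row, says: "Blood work may be obtained +/-5 days from the next treatment day for logistical and scheduling purposes".

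**First dose.** Section 2.4 is strict: "All subjects are required to complete baseline evaluations within 1 day prior to the first planned dosing of the study drug". I found no matching rule for later doses.

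**Dosing windows.** Footnote p sets the first three doses 21 days apart, plus or minus 3 days, and the boosters "every 8 weeks (56 days: -3 days up to +8 days) intervals thereafter". For an unrelated acute illness, 3.3.1 adds that "delays up to 4 weeks are considered acceptable in this setting".

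**The concern.** A recovery condition protects the patient only if the result exists before the injection. Under footnote m a site can follow the calendar exactly and still give a repeat dose with no laboratory value obtained since the previous one. Abnormalities already detected are followed under 6.1. The exposed case is a new abnormality without symptoms, for example in ALT or platelets, which cannot trigger a hold under 3.3.1 until it is measured.

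The prior evidence is reassuring but limited. In the ETBX-011 trial (11.1.2), the 28 patients who received all three doses showed no laboratory change judged biologically important at week 9. That was a single vaccine. The three-vaccine combination has not been given to humans (1.2.10). Its vector load per visit at dose level 1 is three times the highest ETBX-011 dose, which only 6 patients received.

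There is also a smaller analytic cost. A late draw comes after two doses, which blurs the tabulation of adverse events by treatment planned in 8.4.4.

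**Working it through.** The plan gives no figure to reproduce. The check compares the texts and counts days.

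**Inputs**
- Draw window at a repeat-dose visit: −5 to +5 days (3.4, footnote m).
- Baseline draw: 0 to 1 day before dose 1 (2.4).
- Interval between the first three doses: 21 days, at most 21 + 3 = 24 (footnote p).
- Interval before a booster: 56 days, at most 56 + 8 = 64 (footnote p).
- Dose level 1: 5×10¹¹ VP of each of three vaccines (Précis). Highest ETBX-011 dose: 5×10¹¹ VP (11.1.2).

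**Step 1: the window against the injection.** For an injection on day 21, the permitted draw runs from day 21 − 5 = 16 to day 21 + 5 = 26. Days 22 to 26 fall after the dose that depends on the result.

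**Step 2: when the interval result is missing.** A repeat dose lacks one only if the previous visit's draw was on or before its injection and this visit's draw is after its injection. Then:

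age of last result = dosing interval + days by which the previous draw preceded its injection

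| Dose | On schedule | Oldest at footnote p's upper limit |
|---|---|---|
| Week 3 | 21 + 0 to 21 + 1 = 21 to 22 days | 24 + 1 = 25 days |
| Week 6 | 21 + 0 to 21 + 5 = 21 to 26 days | 24 + 5 = 29 days |
| Booster | 56 + 0 to 56 + 5 = 56 to 61 days | 64 + 5 = 69 days |

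**Step 3: a site that always draws at +5.** Week 3 has no interval result, because the baseline draw precedes dose 1. Later doses do have one, but it is old:
- Week 6: 21 − 5 = 16 days (24 − 5 = 19 at the upper limit).
- Booster: 56 − 5 = 51 days (64 − 5 = 59 at the upper limit).

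**Step 4: which doses 3.3.1 governs.** Section 3.1.1 gives both a 28-day DLT definition and a 1-week evaluation period for de-escalation. Week 6 and the boosters lie beyond both. Week 3 (day 21) lies beyond the 1-week period, but its status is unclear on the 28-day reading.

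**Step 5: vector load.** 3 × 5×10¹¹ = 1.5×10¹² VP per visit. The ratio to the highest ETBX-011 dose is 1.5×10¹² / 5×10¹¹ = 3.

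**Step 6: with a −5 to 0 window.** The draw for a day-21 injection falls on days 16 to 21, so the result is 0 to 5 days old at every repeat dose.

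**The case against.** The strongest reply is that the two texts can both be obeyed. Section 3.3.1 is mandatory and footnote m only permissive, and tumor imaging has almost the same 5-day tolerance (footnote h). A careful site would use the late side only when no recovery question is open. Nor does 3.3.1 expressly demand a fresh result before each dose. This stands as a reading, but nothing in the text imposes it, and it does not cover a new, silent abnormality: no recovery question is open because nobody has looked. Imaging differs because it is not part of the recovery condition.

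Second, other safeguards exist. Each repeat-dose visit includes physical examination, vital signs and adverse-event review, and the team discusses each patient (7.6.1). Many silent laboratory changes would also fall outside the DLT definition (3.1.1) or the adverse-event criteria (6.1). These points lower the likely harm. They do not detect a silent change, and one the investigator judges significant would still count as an adverse event.

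Third, the effect is narrow. A site that always draws late misses an interval result only at week 3, and at no dose governed by 3.3.1 if week 3 is excluded on the 28-day reading. A gap at week 6 or a booster needs an early draw at one visit and a late one at the next. This stands, and it limits the size of the problem.

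Fourth, the day counts measure the window from the actual injection. If the footnote means the planned day, a +5 draw would precede a booster given at +8 by 8 − 5 = 3 days, and some counts for delayed doses change. On-schedule doses are unaffected. A 3-weekly dose given at +3 would still precede a draw at +4 or +5.

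Finally, footnote m is marked only on the chemistry row. Its general wording about blood work probably reaches the CBC, but that is an inference.

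**Conclusion.** The concern holds. The plan makes re-dosing depend on laboratory recovery but lets the only scheduled chemistry, and probably the CBC, be drawn after the dose. It should be fixed because safety is the primary objective and the combination is new to humans, though the probability of harm is likely low.

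The size depends on site practice, which the documents do not describe. At worst with on-schedule dosing, the last result is 22 days old at week 3, 26 at week 6 and 61 at a booster. The upper-limit figures of 25, 29 and 69 days are not maxima, because 3.3.1 also accepts illness delays and 3.2.4 allows dosing within 7 days of plan. The delayed-dose counts assume that the draw window is measured from the actual injection day. The conclusion for the chemistry panel does not rest on the reading of CBC coverage or of the DLT period.

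**What to change.** Amend footnote m so that scheduled chemistry and CBC for weeks 3 and 6 and each booster are drawn from 5 days before the treatment day up to that day, and are reviewed against 3.3.1 before the injection. State that the footnote covers the CBC. Say that extra post-dose safety draws remain allowed and are not deviations. The recovery grades need no change.

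The cost is one footnote edit in an amendment, somewhat less scheduling flexibility and an occasional wait for same-day results. No chemistry or CBC tests are added.

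One limit: 2.1.1.7 also lists "Prothrombin (PT)-international normalized ratio (INR) < 1.5" and a PTT criterion, but the calendar schedules coagulation tests only at screening and end of treatment. The new window does not supply them. The amendment should say whether 3.3.1 requires them for re-dosing; they add a test only if it does.
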